variables such as neuropsychological measures and inflammatory markers. Generalized linear models (GLM) will be used for the baseline data. We are aware that numerous other confounders exist (such as age, race, education, statin use and gender). When a variable is identified to be related to the outcome and covariate of interest, i.e. confounder, we will adjust for it in the model of choice. A sensitivity analysis of statin and/or ARB use will be performed via analysis by statin and ARB use to determine if it is necessary to adjust or stratify by statin and ARB use. Models consider inclusion of the list of known covariates and their interaction. The importance of these models will be assessed through inspection of the change in the parameter of interest, as well as the parameter (and p-value) for the covariate. Point estimates, p-values, and confidence intervals to test the covariate of interest will be computed. Mixed model diagnostics and GLM diagnostics will be evaluated. For the continuous outcomes, we will assess if transformations exist that can bring about near normality. In addition, the impact of skew on the stability of estimates can be assessed using bootstrap methodology. For all models involving skewed predictors, we will assess the impact of the significant outliers using bootstrap and will check the linearity assumption. Other diagnostic procedures will be used to check for the validity of the GLM assumptions such as normality of the residuals and linearity assumption. Missing data problems are ubiquitous in aging research. Missing values can arise from several sources, (1) subjects are lost to follow-up, (2) missing CRFs, or (3) particular items of a CRF are skipped. We will employ multiple imputation. In this design, we have numerous indicators of outcome and predictors. The concern is that the possibility of a Type-I error is increased if a series of univariate tests is employed. Several solutions are possible in the context of this design: 1) use of Bonferroni Corrections or the less conservative extension to Bonferroni corrections 2) use of data reduction techniques like Principal Component Analysis (PCA) , and 3) use of multivariate mixed models. Based on the estimated numbers of remitters vs non-remitters we expect to enter approximately 53 subjects in Phase II. Using the estimates from Abbasi et al. (7) for serum IL-6 comparing SSRI+celecoxib to SSRI+placebo, we will have greater than 95% power by randomizing the 53 subjects between the two groups.

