### 6.3 Analysis of Specific Aims

Aim 1: Characterize neuroanatomical and neuropsychological effects of abnormal cytokines in MDD. Hypothesis 1a: Inflammatory cytokines will be elevated centrally and peripherally relative to matched controls; neuropsychological performance will be poorer in MDD; hippocampus and amygdala volumes and PFC thickness will be decreased in MDD; and connectivity of hippocampus and amygdala will be decreased in MDD (hippocampus to DLPFC and AC; amygdala to subgenual AC). For an unadjusted analysis, a t-test can be utilized to assess depression group differences among the various outcomes. Linear regression will be used to assess whether various outcomes differ between depression status adjusting for confounders (such as age, race, education, statin use, and gender). Baseline inflammatory cytokines, neuropsychological measures, functional connectivity, and volumetric data will be treated as outcomes in the linear regression model with depression status as a covariate as well as possible other confounders as covariates.

Hypothesis 1b: Cytokine levels will be correlated with hippocampal and amygdala volumes and PFC thickness; we predict that higher IL-6 and lower IL-10 will be correlated with decreased hippocampal and amygdalar volumes and decreased PFC thickness. The Pearson moment-product correlation coefficient (or Spearmans rank correlation coefficient when normality assumptions are violated) will be used to assess relationships between cytokines and ROI measures for an unadjusted analysis. Linear regression will be used to assess whether the ROI data are related to the inflammatory markers, while adjusting for depression status and confounders. In addition, we will confirm whether an interaction term between the inflammatory markers and depression is necessary.

Hypothesis 1c: There will be a correlation between cumulative duration of depression and volume loss in hippocampus and amygdala, particularly hippocampus CA2-3. We will correlate the lifetime history of depression with hippocampal and amygdala volumes and predict a significant correlation using the Pearson product-moment correlation coefficient or Spearman rank correlation coefficient depending on normality assumptions.

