Aim 2: Characterize the reversibility of brain dysfunction, including cognitive impairment with treatment of depression and its association with inflammation. Hypothesis 2a: Subjects randomized to treatment will have greater normalization of IL-6 and IL-10, greater improvements in memory, executive function and improvements in resting state functional connectivity compared to those randomized to placebo. For an unadjusted analysis, a paired t-test can be used to determine if there is a difference in the pre-treatment and post-treatment inflammatory cytokines. Mixed models will be utilized to assess if the inflammatory markers change over time adjusting for confounders. A mediator analysis will be utilized to determine whether MADRS has an effect independent of treatment on the inflammatory levels. The first

CONFIDENTIAL

approach would be to test for an interaction effect between baseline MADRS and treatment in a mixed model with inflammatory markers as the outcome adjusting for MADRS, treatment, and an interaction between MADRS and treatment. If the interaction term is not significant we will determine if MADRS independently of treatment or additively with treatment is related to inflammatory markers. Structural equation models can be an alternative approach for the mediator analysis.

Hypothesis 2b: Improvement in clinical depressive scores post treatment will be correlated with changes in cytokine levels. Change score models or joint mixed models will be utilized to assess the relationship between depression scores (outcome) and inflammatory markers, while adjusting for confounders in the depressed subjects.

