**Framingham 10-year risk score of 13 (15% 10-year risk), taking into consideration that the 10-year cardiovascular risk in our elderly age group (age 60-80) is estimated at 13.5% in the general population and 15% in patients with cerebrovascular risk factors, and ii) to reduce the upper age for inclusion to 80 years of age..** The feasibility of this approach is drawn from our pilot data in a sample (n=217) of late life depression and controls where we determined the Framingham score in both patients with MDD (who had higher vascular risk scores) and age matched controls: Age 60-65 mean score MDD: 9.0 (10-year stroke risk of 8% vs 7% for general population). Age 65-74 mean score: 12.2 (10-year risk of 13.5% vs average risk = 11%); 75-84 mean score: 16.2 (10-year risk of 23% vs average risk of 20%).

**To explore retrospectively how adverse events relate to differences in drug effects, i.e. inhibition of prostaglandin synthesis, urine spot samples will be collected for prostaglandin metabolite analysis at select time points optionally.**

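### Section 6.1's data-driven covariate rule is not confined to the MDD-versus-control aim; the randomised celecoxib comparison needs a model fixed before unblinding

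*Combined protocol and SAP*

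**What the plan says.** Section 6.1 gives one model-building rule for the whole analysis.

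- **Entry:** "When a variable is identified to be related to the outcome and covariate of interest, i.e. confounder, we will adjust for it".
- **Judging models:** their importance is to be "assessed through inspection of the change in the parameter of interest, as well as the parameter (and p-value) for the covariate". No cut-off or order of selection is given.
- **Candidates:** the list is open, since "numerous other confounders exist (such as age, race, education, statin use and gender". ARB use comes in separately, through a sensitivity analysis meant "to determine if it is necessary to adjust or stratify by statin and ARB use".
- **Interactions:** "Models consider inclusion of the list of known covariates and their interaction".

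Section 6.3 repeats the confounder list for Hypothesis 1a. For Hypothesis 2a, worded as "Subjects randomized to treatment will have greater normalization of IL-6 and IL-10" than those given placebo, it calls for mixed models with confounder adjustment and lists no covariates. Hypothesis 2c (section 1.1), on adding celecoxib versus placebo, has no analysis of its own in section 6.3.

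Some things are settled. Baseline MADRS is a fixed covariate for the MADRS outcome (sections 2.1 and 6.2). Section 2.7 describes a group-by-time repeated measures ANOVA for connectivity and names no covariates. CRP level, by which depressed participants are stratified (sections 1.1 and 2.2), appears nowhere in section 6 as a model term.

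**The concern.** Confounder selection answers an observational question. For MDD versus controls, a variable related to both group and outcome can bias the comparison, so looking for such variables makes sense. Between randomised arms, any association between a baseline variable and arm is due to chance, and the test's 5% level already allows for it.

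Applied to the arms, the rule has three drawbacks:

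- It has no bias to remove.
- It admits a covariate because of chance imbalance rather than because it predicts the outcome, so a strong but balanced predictor can stay out. That can include the CRP stratum, or the baseline value for outcomes other than MADRS.
- With no threshold and an open list, the model is settled after the arm effect has been seen to move. The nominal 5% level and the interval coverage then depend on how the analyst uses that freedom.

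**Working it through.** **1. The plan's own figure.** Section 2.7 powers the Hypothesis 2a IL-6 comparison with a two-sided t-test at 5%, difference 2.1, SD 3.6, 50 per group.
- Standard error = 3.6 × √(2/50) = 0.72, and 2.1/0.72 = 2.92.
- Power ≈ Φ(2.92 − 1.96) = 0.83 (exact t-test 0.82). The 80% claim reproduces; 48 per arm would be enough.
- With 10% attrition (stated in section 2.7 for the connectivity test), 50 × 0.9 = 45 per arm, and power is 0.79 (exact t-test 0.78).

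So the stated power belongs to a test whose 5% level is taken as given. The question is what the section 6.1 rule does to that level.

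**2. Type I error by simulation.** No closed formula applies. The set-up is no arm effect, 45 per arm, linear regression, and six independent covariates (the number named: age, race, education, statin use, gender, ARB use). Each is assumed to correlate .2 or .3 with the outcome, so together they explain 6 × .2² = .24 or 6 × .3² = .54 of the variance. The cut-offs are assumptions, because the plan gives none. With 3,000 trials the Monte Carlo standard error near 5% is √(.05 × .95/3,000) = 0.4 points.

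| How covariates are chosen | Rejection at .05 |
|---|---|
| All six, fixed in advance | 4.6–5.5% |
| Keep if covariate p < .05 | 5.6–5.9% |
| Related to outcome and arm, cut-off .05 | 4.2–4.3% |
| Related to outcome and arm, cut-off .20 | 2.8–3.8% |
| Arm estimate moves by more than 10% | 3.7–4.8% |
| Smallest treatment p over eight models (unadjusted, six single-covariate, full) | 9.7–13.3% |

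**3. Sensitivity to the assumptions.** A second simulation used 50 per arm, 2,500 trials per setting, and joint covariate R² from 0 to .5.
- Fixed set: 4.6–5.0%. Unadjusted: 4.5–4.9%.
- Mechanical rules (covariate p, 10% change in estimate, or either): 3.0–5.8%.
- Smallest treatment p over all 2⁶ = 64 subsets: 7.0% at R² = 0, rising to 22.0% at R² = .5.

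The last figure shows that the worst case depends on how many models are searched. Choices over interactions were not simulated.

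**4. Precision.** Section 2.7 assumes an intraclass correlation of .7 for connectivity. If that is the correlation between baseline and follow-up, with equal variances, the relative error variance is:
- follow-up value alone: 1.00;
- change score, which the group-by-time test uses: 2 × (1 − .7) = .60;
- follow-up adjusted for baseline: 1 − .7² = .51.

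A fixed baseline covariate is therefore worth having for every outcome, whether or not baseline happens to differ between arms.

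**The case against.** The best counter-argument is about scope. Section 6.1 opens by naming depression status as the single between-person factor, and section 6.3 uses the same confounder list for Hypothesis 1a. On that reading the covariate of interest is MDD status, where choosing confounders is legitimate. The sentence on inspecting models mentions no arms, and the adjustment sentence under Hypothesis 2a concerns change over time. This stands in part: reaching the arms is an inference from the rule's general scope and from where the Hypothesis 2a sentence sits. But the text sets no limit, and no other rule covers Hypothesis 2c.

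A reader might infer that the treatment test will be tuned until it is significant. The documents do not support that. The only p-value in the inspection sentence is the covariate's, and nothing says a model is picked by the treatment p-value. The 9.7–13.3% row bounds that conduct over eight models; it does not describe the plan.

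A reader might also infer that vascular risk will be wrongly dropped from the case-control analyses, since section 10.5.1 reports "patients with MDD (who had higher vascular risk scores". That does not follow either. The list is open, and section 2.5 matches controls on vascular risk factors. The pilot was a late-life sample with controls described only as age-matched, so its imbalance need not recur here.

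Parts of the remedy already exist. Baseline MADRS is fixed, section 6.1 allows control for baseline through residualised change, and section 6.3 states unadjusted analyses for Hypotheses 1a and 1b. For Hypothesis 2a, though, the unadjusted analysis in section 6.3 is a paired pre-post test, not a comparison of arms.

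**Conclusion.** The point holds for the randomised comparison, at moderate weight. The section 6.1 rule has no purpose between randomised arms, can leave out prognostic terms including the CRP stratum, and does not guarantee the 5% level. Applied mechanically it does little damage: about 3 to 6% against a nominal 5%, and the entry rule as written falls at or below nominal. The larger figures need selection on the treatment result, which the plan does not state. All the simulated sizes rest on assumed covariate strengths, independence between covariates, and assumed cut-offs, none of which the documents supply.

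For the MDD-versus-control analyses, data-driven confounder adjustment is a matter of judgement and is not faulted here.

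**What to change.** For the randomised comparison (Hypotheses 2a and 2c), delete the inspection and confounder-selection rule. Before unblinding, fix one model per outcome: arm + baseline value of that outcome + CRP stratum (≥3 versus <3), plus any prognostic covariates, such as age and sex, named in advance. Report the unadjusted arm comparison beside it. Any statin or ARB analysis of the arms should be labelled as sensitivity and should not change the main model. Because placebo non-remitters move to open-label celecoxib at week 6 (section 2.2), some assignments become known while the trial runs, so the model is best fixed and dated now.

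Confounder adjustment may stay for the observational MDD-versus-control analyses. Adding the Framingham score, already collected and reflecting a matching factor, to the named list is optional and mainly a gain in precision. It rises with age in the pilot (9.0, 12.2, 16.2 across age bands), so entering both needs a reason.

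The cost is SAP wording and two or more degrees of freedom. With 90 completers, residual degrees of freedom go from 90 − 2 = 88 to 90 − 4 = 86, or 84 with age and sex. No new data are needed.

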
## 6.2 Variables to be used in hypothesis testing

- 1) For measure of cytokine levels we will measure these in CSF and blood: Primary measure IL-6 pre- and post-treatment.
- 2) Hippocampus, including subvolume analyses and Amygdala volumes: Left and right volumes will be separately measured and standardized by cortical volumes before being entered in analyses. Prefrontal cortical thickness: L & R orbitofrontal, superior frontal and frontal pole.
- 3) Antidepressant treatment response determined using the MADRS score following antidepressant treatment covaried on baseline MADRS score.
- 4) Neuropsychological function as determined by factor scores from episodic memory and executive function.

CONFIDENTIAL

5) Resting state functional connectivity of the hippocampus and amygdala to anterior cingulate (AC) and dorsolateral prefrontal cortex (DLPFC).

### 6.3 Analysis of Specific Aims

Aim 1: Characterize neuroanatomical and neuropsychological effects of abnormal cytokines in MDD. Hypothesis 1a: Inflammatory cytokines will be elevated centrally and peripherally relative to matched controls; neuropsychological performance will be poorer in MDD; hippocampus and amygdala volumes and PFC thickness will be decreased in MDD; and connectivity of hippocampus and amygdala will be decreased in MDD (hippocampus to DLPFC and AC; amygdala to subgenual AC). For an unadjusted analysis, a t-test can be utilized to assess depression group differences among the various outcomes. Linear regression will be used to assess whether various outcomes differ between depression status adjusting for confounders (such as age, race, education, statin use, and gender). Baseline inflammatory cytokines, neuropsychological measures, functional connectivity, and volumetric data will be treated as outcomes in the linear regression model with depression status as a covariate as well as possible other confounders as covariates.

Hypothesis 1b: Cytokine levels will be correlated with hippocampal and amygdala volumes and PFC thickness; we predict that higher IL-6 and lower IL-10 will be correlated with decreased hippocampal and amygdalar volumes and decreased PFC thickness. The Pearson moment-product correlation coefficient (or Spearmans rank correlation coefficient when normality assumptions are violated) will be used to assess relationships between cytokines and ROI measures for an unadjusted analysis. Linear regression will be used to assess whether the ROI data are related to the inflammatory markers, while adjusting for depression status and confounders. In addition, we will confirm whether an interaction term between the inflammatory markers and depression is necessary.

Hypothesis 1c: There will be a correlation between cumulative duration of depression and volume loss in hippocampus and amygdala, particularly hippocampus CA2-3. We will correlate the lifetime history of depression with hippocampal and amygdala volumes and predict a significant correlation using the Pearson product-moment correlation coefficient or Spearman rank correlation coefficient depending on normality assumptions.

Aim 2: Characterize the reversibility of brain dysfunction, including cognitive impairment with treatment of depression and its association with inflammation. Hypothesis 2a: Subjects randomized to treatment will have greater normalization of IL-6 and IL-10, greater improvements in memory, executive function and improvements in resting state functional connectivity compared to those randomized to placebo. For an unadjusted analysis, a paired t-test can be used to determine if there is a difference in the pre-treatment and post-treatment inflammatory cytokines. Mixed models will be utilized to assess if the inflammatory markers change over time adjusting for confounders. A mediator analysis will be utilized to determine whether MADRS has an effect independent of treatment on the inflammatory levels. The first

CONFIDENTIAL

approach would be to test for an interaction effect between baseline MADRS and treatment in a mixed model with inflammatory markers as the outcome adjusting for MADRS, treatment, and an interaction between MADRS and treatment. If the interaction term is not significant we will determine if MADRS independently of treatment or additively with treatment is related to inflammatory markers. Structural equation models can be an alternative approach for the mediator analysis.

Hypothesis 2b: Improvement in clinical depressive scores post treatment will be correlated with changes in cytokine levels. Change score models or joint mixed models will be utilized to assess the relationship between depression scores (outcome) and inflammatory markers, while adjusting for confounders in the depressed subjects.

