### **2.5 Target population**

One-hundred depressed subjects, aged 18-80, right handed, male and female (50 with high-CRP levels ( $CRP \geq 3$ ) and 50 with low-CRP levels ( $CRP < 3$ )). In addition, 50 non-depressed controls, matched on demographic and vascular risk factors.

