## **2.8 Key inclusion criteria**

Inclusion Criteria for all Participants:

- 1) Age 18-80, right-handed male or female, any race;
- 2) Absence of clinical dementia
- 3) English speaking
- 4) Blood pressure not exceeding 150/90 mmHg, treated or untreated
- 5) Normal result on liver-function test
- 6) No history of ulcer disease or GI bleeding
- 7) No renal insufficiency
- 8) Weight greater than 110 lbs

Additional Inclusion Criteria for Depressed Participants:

CONFIDENTIAL

- 1) DSM-IV criteria for MDD
- 2) PHQ-8 Score equal to or greater than 10

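### Section 6.3 tests Hypothesis 1c only by an unadjusted correlation of depression duration with brain volumes over ages 18-80 and does not carry the age adjustment of 6.1 into it

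*Combined protocol and SAP*

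**What the plan says.** Section 6.3 states Hypothesis 1c as "There will be a correlation between cumulative duration of depression and volume loss in hippocampus and amygdala, particularly hippocampus CA2-3". The analysis is "We will correlate the lifetime history of depression with hippocampal and amygdala volumes and predict a significant correlation", carried out "using the Pearson product-moment correlation coefficient or Spearman rank correlation coefficient depending on normality assumptions". No covariate, partial correlation or regression is mentioned.

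The two neighbouring hypotheses in 6.3 are handled differently. Each has a simple test that is labelled unadjusted, followed by an adjusted model. For 1a the model is a linear regression of the baseline outcomes, including the volumes, on depression status, with age first in the list of confounders. For 1b, "Linear regression will be used to assess whether the ROI data are related to the inflammatory markers, while adjusting for depression status and confounders".

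Section 6.1 contains general statements that bear on this. It says: "We are aware that numerous other confounders exist (such as age, race, education, statin use and gender"). It assigns generalized linear models to the baseline data, and it says that a variable found to be related to both the outcome and the covariate of interest will be adjusted for in whichever model is chosen.

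The depressed sample is described in section 2.5 as "One-hundred depressed subjects, aged 18-80, right handed, male and female". Volumes are standardized before analysis, by brain volume in 2.1 and by cortical volume in 6.2.

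**The concern.** Years of lifetime depression cannot exceed years lived, so duration and age can be expected to rise together in a sample that runs from 18 to 80. If standardized hippocampal or amygdala volume also falls with age, age is a common cause of longer duration and smaller volume. The unadjusted coefficient then tends to be negative, as 1c predicts, even if duration has no effect.

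What is at stake is the interpretation. Section 1.2 sets out the idea that repeated depressive episodes lead to progressive regional loss in the brain. A significant negative coefficient would be read as support for it, and the named test cannot separate that explanation from ageing. The plan itself treats age as relevant to these volumes under 1a, and Hypothesis 1d in section 1.1 expects an age interaction with depression.

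**Working it through.** **Inputs from the documents**
- Test for 1c: Pearson or Spearman, no covariates (6.3).
- Depressed participants: 100, aged 18-80 (2.5).
- Two-sided 5% level and 80% power. These are stated in 2.7 for 1b; 2.7 gives no power statement for 1c.

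**Inputs that are assumptions**
- The age-duration correlation a and the age-volume correlation b. The documents give neither, so a range is shown.
- The 1c analysis uses the 100 depressed participants. Section 6.3 does not say so outright.

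**Step 1. Reproduce the plan's own correlation figure.** Section 2.7 gives a detectable correlation of |.23| for 1b with 150 subjects. By Fisher's transformation:

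r = tanh[(1.960 + 0.842)/√(n − 3)] = tanh(2.802/√147) = tanh(0.231) = .227

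This rounds to .23, so the method matches the plan's. For n = 100, the detectable |r| is tanh(2.802/√97) = .277, and the two-sided critical |r| is tanh(1.960/√97) = .196.

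**Step 2. Correlation produced by age alone.** If duration has no effect on volume once age is held fixed, and the relations are linear, the unadjusted correlation is r = a × b.

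**Step 3. Chance that this is declared significant at n = 100.** Let m = atanh(|r|) × √97. The chance in the predicted negative direction is Φ(m − 1.960). The two-sided chance adds Φ(−m − 1.960).

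| a | b | r = a × b | m | Predicted direction | Two-sided |
|---|---|---|---|---|---|
| .3 | −.2 | −.06 | 0.592 | 8.6% | 9.1% |
| .3 | −.3 | −.09 | 0.889 | 14.2% | 14.4% |
| .4 | −.3 | −.12 | 1.188 | 22.0% | 22.1% |
| .4 | −.4 | −.16 | 1.589 | 35.6% | 35.6% |
| .5 | −.4 | −.20 | 1.997 | 51.5% | 51.5% |
| .5 | −.5 | −.25 | 2.516 | 71.1% | 71.1% |

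The nominal values are 2.5% in one direction and 5% two-sided.

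**Step 4. Simulation check.** There were 3,000 replicates of n = 100, with age uniform on 18-80 and duration a random fraction of the years since age 12. Volume depended linearly on age and not on duration. The age-duration correlation came out at about .49.

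| Age-volume correlation | Pearson | Spearman | Age partialled out |
|---|---|---|---|
| 0 | 5.6% | 5.8% | 5.2% |
| −.2 | 15.3% | 14.5% | 5.2% |
| −.3 | 30.6% | 30.1% | 4.7% |
| −.4 | 50.9% | 49.5% | 4.5% |
| −.5 | 70.1% | 68.8% | 5.4% |
| −.6 | 86.6% | 86.0% | 4.9% |

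Switching to Spearman does not help. Holding age fixed brings the rejection rate back to nominal throughout.

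**Step 5. Power cost of adjusting.** With k covariates the divisor becomes √(n − k − 3). At n = 100 the detectable correlation moves from .277 (k = 0) to tanh(2.802/√96) = .278 with age, and to tanh(2.802/√92) = .284 with five covariates.

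**The case against.** The strongest reply is that the plan already deals with age. Section 6.1 names it as a confounder, gives generalized linear models to the baseline data (which include the volumes), and promises adjustment when a variable is related to both outcome and covariate. Age would meet that condition in exactly the scenario assumed above. This stands in part. A reader might infer from 6.3 that the plan overlooks age, or that 1c has no model in which to adjust for it; 6.1 does not support either reading. What remains is that the specific text for 1c names a coefficient without covariates. The authors repeated the adjustment for 1a and 1b despite the general rule and did not for 1c, and the rule depends on what is found in the data. Even on a generous reading, 1c has two candidate analyses and nothing to say which one decides it.

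The second reply concerns size. Standardizing by brain or cortical volume may weaken the age-volume link, because the denominator may itself fall with age. So may the eligibility limits: no Clinical Dementia Rating above 0 and no primary neurological disorder (2.9), a Mini-Mental score of at least 26 (5.3), and the Framingham ceiling described in 10.5.1. This stands: the upper rows of the table are uncertain. Neither feature adjusts for age, however, and neither removes the confounding.

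Third, 1c is a cross-sectional baseline association. It does not affect randomization, the celecoxib comparison or safety. That is correct and limits the severity.

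**Conclusion.** The concern holds in a limited form. The test that 6.3 names for 1c can return the predicted result from ageing alone, because the general rule of 6.1 is not carried into it. With no true duration effect, the chance of a significant result runs from about 9% to 71% over the age-duration and age-volume correlations tried. Those correlations are assumptions, as are linearity and the use of the 100 depressed participants only.

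A reader might take 36% to 71% as the error rate of this trial. The documents do not support that: those values need correlations of .4 to .5 in size on both sides, and with weaker links the inflation is modest. If controls were included with duration zero, diagnosis would be a further confounder and these figures would not apply directly.

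This is a should-fix point. It concerns a stated hypothesis on volumes that 2.1 lists among the primary outcome variables, but it can be corrected at any time before analysis without changing how the trial is run.

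**What to change.** In 6.3, make the test of 1c a linear regression, or the equivalent partial correlation, of each standardized volume on cumulative depression duration in the depressed participants. Prespecify age as a covariate whatever the data show, check its linearity, and include the other confounders of 6.1 such as gender. Report the raw Pearson or Spearman coefficient as descriptive only.

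Keep the existing volume standardization and do not also enter its denominator as a covariate, since that would adjust for size twice.

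The cost is a sentence or two in 6.3. Age is known from eligibility and lifetime depression is recorded at baseline (12.1), so the main adjustment needs no new data. The loss of power is negligible, as step 5 of the working shows.
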